The aim of this study is to assess the effect of the application of regular, mid-frequent electrotherapy on chronic neck- or low-back pain. This electrode mat used in the study is larger than the electrode patches of conventional TENS devices, and covers the entire spine. The patients are interviewed anamnesticly and physically examined before and after the application of the device regarding the subjective pain sensation (Numeric pain rating scale, Shortform-Mc Gill Pain Questionnaire incl. Visual analogue scale) and the functionality in everyday life using questionnaires (Roland-Morris Disability Questionnaire, Neck Disability Index). Furthermore, the spine mobility (i.e. the range of motion) of the cervical and lumbar region is also determined before and after the sessions.

Type of the study

The study is a prospective, monocentric, double-blind, randomized and controlled study.

Primary outcome:

- Is there a significant difference in the Visual Analogue Scale (VAS)/Numeric rating scale (NRS) of patients with neck- and low-back pain before and after application of StimaWELL® between verum, control group, and control of the control group)?

Secondary outcomes:

- Is there a significant difference in the individual pain qualities (SF-MPQ), in the Roland-Morris Disability Questionnaire, in the Neck Disability Index, in the spinal range of motion (ROM) in chronic neck- or low-back pain patients after application of StimaWELL® compared to the control group and control of control group?

- Are there gender-specific differences regarding the effect of StimaWELL® regarding SF-MPQ, in the Roland-Morris Disability Index, Neck-Disability Index or ROM?

- Does the use of StimaWELL® change the need for painkillers (WHO level II, WHO level III drugs)?

Material and methods

The study will test 125 patients (equivalent to 50 patients in the verum group, 50 patients in the control group, as well as 25 patients in control of the control group) in the pain outpatient clinic of the University Clinic for Anesthesia, General Anesthesia and Special Pain Therapy. The patients are recruited from the respective outpatient clinics, by extramural ordinations or libraries by means of flyers, and were asked to contact the e-mail address [contact] for preliminary examination. As a next step they are randomized into three different groups: "Verum group" with superliminal mid-frequency stimulation for 30 min after device calibration, "control group" with Sham treatment with device calibration only without consequent electrostimulation, or "control of the control group" without any stimulation. During the preliminary examination, all patients, regardless whether they have been recruited by public libraries or extramural ordinations, are examined by trained medical staff in respect to the inclusion and exclusion criteria. Patients who are eligible to participate in the study are then assigned to the six-time weekly sessions for 30 min each, and for follow-up examination.

The recruitment of patients were performed in the pain clinic of the University Clinic for Anesthesia, in the University Clinic for Physical Medicine and Rehabilitation in the Medical University of Vienna, as well as by the following extramural ordinations and public libraries by means of advertising flyers:

- University Library of the Medical University of Vienna

- Entrance hall/pinboards on level 5 and pinboards on level 4, levels 7 and 8 of the Medical University of Vienna
- Orthopaedics Donauzentrum [name]/[name], [name]
- [name], ENTObere Landstraße 3, 3500 Krems
- [name], [name], [name]
- [name], [name], [contact]
- [name], [name], [contact]
- [name], [name], [contact]
- [name], [name], [contact]
- Medical Councillor [name], [name], [contact]
- [name], [name], [contact]
- [name] [name], [name], [contact]
- [name], [name], [contact]
- [name], [name], [contact]
- Medical Councillor [name], [name], [contact]

- Neuropathic, radicular pain (anamnestic query)
- Acute instabilities and/or surgical indication in the spine (e. g. sudden loss of strength, acute problems with urination or defecation, riding pants hypoesthesia)
- Previous spine surgery
- Infections/abscesses/skin lesions in the spine or the surrounding area
- Malignant diseases or secondary blastomas in the spine or in the surrounding area
- Change in the pain therapy the last 4 weeks (e. g. intravenous infusions, local infiltrations, peridural anesthesia or other invasive procedures in the close vicinity of the spine, physical treatments, change of the oral drug therapy)
- Cardiac arrhythmias, implanted pacemaker or defibrillator, previous heart surgery
- Epilepsy

Management of complications and aftercare

Patients receive a written information sheet with the contact details of the study leaders in order to be able to report any undesirable effect.

Benefits for study participants

The advantage of the patients is the intensified medical and physical care during the study, as well as the option to receive further treatments with StimaWELL® in the Pain Outpatient Clinic after the study participation.

Ethical considerations

StimaWELL® is a form of electrotherapy, based on the TENS device widely used in everyday clinical practice, and is not-invasive, cost-effective, easy to perform, low side effect, and takes only approx. 30 minutes per application. Analogous to the TENS device, a painkiller requirement reducing effect is expected after repeated application.

The duration of the total examination of about one hour and follow-up evaluation of 60 minutes each, as well as 6 therapy units of 30 minutes per patient at weekly intervals, can be regarded as less stressful.

There are no additional invasive measures beyond the normal outpatient measures (e.g. X-ray examination, blood sampling). For these reasons, no risks for the study participants are to be expected.

The consent of the study participants is given by means of an information sheet and detailed oral information.

Time shedule

All examinations (anamnesis incl. personal data collection and assessment of the past medical history, physical examination, questionnaires about the functionality in daily life, quality of life, and measurement of the spine mobility) can be carried out within about an hour in total. The application of StimaWELL® does not exceed about an hour (about 30 minutes on average).

Actionn	Number of treatments/sessions	Required time
anamnesis	1x	about 10 minutes
Survey of the subj. Pain perception by means of questionnaire (SF-MPQ incl. VAS)	2x (before and after 6 units StimaWELL®)	about 10 minutes
Survey of functionality in everyday life by means of questionnaires (Roland-Morris Disability Questionnaire, Neck Disability Index)	2x (before and after 6 units StimaWELL®)	about 20 minutes
Examination of the spinal mobility (ROM)	2x (before and after 6 units StimaWELL®)	about 10 minutes
Application of StimaWELL® or Sham treatment	6x	about 30 minutes
Evaluation of medication intake	2x (before and after 6 units StimaWELL®)	about 5 minutes

Time Shedule

	Week 1	Week 2	Week 3	Week 4	Week 5	Week 6	Week 7	Week 8
First contact in the outpatient clinic, patient recruitment	Basic investigation (SF-MPQ incl. VAS/NRS, ROM, RMDQ, NDI, medication)							Final investigation (SF-MPQ incl. VAS, ROM, RMDQ, NDI, medication)
		Session 1 (verum/control/control of control)	Session 2 (verum/control/control of control)	Session 3 (verum/control/control of control)	Session 4 (verum/control/control of control)	Session 5 (verum/control/control of control)	Session 6 (verum/control/control of control)	

Study-related measures

At the beginning of the study, a detailed explanation is performed by means of an information sheet and an informed consent is obtained. After a basic investigation (anamnesis inkl. collection of personal data and medical history, physical examination and questionnaires), patients were randomized into one of the three groups (verum, control, control of control). Weekly sessions without or with electrostimulation for 30 min each and six times in total are then performed. In the end, the same investigations performed at the beginning of the study are repeated and patients were asked for any involuntary effects during the study. The basic, as well as the final investigation consist of the following:

Evaluation of personal data and medical history

- Collection of personal data
- Evaluation of the actual pain state (in rest, under activity, average in the last 4 weeks, minimum, maximum) using NRS
- Current or previous illnesses or surgeries
- Concomitant medication

Questionnaires for recording the quality of life (QoL), subjective pain perception and functionality

The survey of the quality of life, the subjective sensation of pain, as well as the functionality in everyday life is carried out with the means of validated questionnaires (SF-MPQ: subjective pain relief; Roland-Morris Disability Questionnaire/Neck Disability Index: Questioning functionality in everyday life). The mobility (range of motion) of the cervical and lumbar spine is based on validated tests (modified-modified Schober: Williams et al., 1993; Tousignant et al., 2005; Performance Attainment Associates CROM: see Tousignant et al., 2000; Williams et al., 2010).

Application of StimaWELL®

StimaWELL® is a multidimensional, dynamic deep stimulation device from Schwa-medico, which is an electrode mat consisting of 12 bilateral stimulation bars. Mid-frequent electrotherapy (2-6 kHz) can be applied, also in combination with heat application and mechanical stimulation (massage) if desired. According to the company, StimaWELL® can be used in acute and chronic pain in the spine with or without degenerations detectable in X-ray or MRI such as osteochondrosis, spondylarthrosis, spondylolisthesis, intervertebral disc protrusions, lumbar spinal canal stenosis, as well as in osteoporosis.

In accordance with the Medical Devices Directive 93/42/EEC, the device bears the CE marking CE0482. StimaWELL® is used in the study according to the indication specified by the manufacturer, namely pain treatment in the spine area, in consideration of the contraindications (see exclusion criteria).

Patients who have been assigned into the verum group receive a suprathreshold stimulation for 30 minutes in each session, which remains subjectively clearly noticeable. In the control group, the device is initially set for device calibration and then switched off (= sham therapy), in the control of control group, the device is kept inactivated from start to finish of the session; to avoid unblinding of the patient, the display is covered with a blanket after device setting so that it can't be seen by the patients.

Statistical analysis

Data is evaluated using Sigma Plot version 12.0 from Systat Software GmbH and SPSS® version 19 from IBM. The demographic data are divided into the following variables and presented:

- Qualitative variables (e.B. gender): absolute frequency in %, calculated separately for verum control and control of the control group
- Quantitative variables (e.B. age, NRS, VAS, ROM): mean + standard deviation, median, minimum, maximum; calculated for verum and control and control of the control group

Primary parameters:

Is there a difference in VAS/NRS between the verum and control group after the application of StimaWELL®?

Mean and standard deviation, minimum, maximum and median for the difference between the pre- and post values are calculated separately for all groups. Statistically significant difference is checked with the help of the t-test for unpaired samples. A significance level of alpha = 5% (two-sided) is used.

Secondary parameters (e.B. differences in the individual pain qualities in the SF-MPQ; gender-specific differences in SF-MPQ, Roland-Morris Test/Neck Disability Index, ROM; Change in drug dosage) are analyzed using RM-One Way ANOVA and Bonferroni correction.

The data of the patients used are pseudonymized. The completeness of the entries (e.B. patient number and initials on each sheet of the CRF) is controlled after testing and transfer to the online form (Clicase) or to Excel developed by the Statistics Institute. The data is transferred to Excel sheets, backed up electronically 2 times at least and printed out once. An interim evaluation in half of the study is planned to check the statistical fluctuation and the dropout rate.

Literature

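### The one-way repeated-measures ANOVA planned for the secondary outcomes is a paired before-after test with no group or gender term, so it cannot answer the between-group and gender questions

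*Combined protocol and SAP*

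**What the plan says.** Under Type of the study, the first secondary outcome asks whether the SF-MPQ pain qualities, Roland-Morris questionnaire (RMDQ), Neck Disability Index (NDI) and range of motion (ROM) differ "after application of StimaWELL® compared to the control group and control of control group". The second begins "Are there gender-specific differences regarding the effect of StimaWELL" and names the same outcomes. A third asks whether the device changes the need for painkillers and names no comparator.

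The table under Time shedule gives the frequency of the SF-MPQ, the functional questionnaires, ROM and medication intake as "2x (before and after 6 units StimaWELL" sessions, that is, two occasions per patient.

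The Statistical analysis section gives the primary parameter a between-group test: "Statistically significant difference is checked with the help of the t-test for unpaired samples". Its secondary paragraph lists "differences in the individual pain qualities in the SF-MPQ", then "gender-specific differences in SF-MPQ, Roland-Morris Test/Neck Disability Index, ROM", and ends "Change in drug dosage) are analyzed using RM-One Way ANOVA and Bonferroni correction". It names no group factor, gender factor or interaction. It does not say which comparisons Bonferroni covers, and no other section supplies a between-group analysis of these outcomes.

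**The concern.** The three groups are parallel and randomised, so group and gender both vary between patients. A one-way repeated-measures ANOVA has one factor, and it varies within patients; here that can only be time. The test therefore asks whether patients changed, not whether verum patients changed more than controls or whether the effect differs by sex.

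The likely harm is false attribution. Patients enter with pain above 5 out of 10, and both control groups attend sessions made to look like treatment. Improvement in every arm, through regression to the mean or non-specific response, is plausible. The named test would call it significant. It can also miss a real difference between arms when their changes offset one another.

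**Working it through.** **The plan's own figure.** The only reproducible calculation is the primary sample size: difference in change 1 point, SD 1.5, power 80%, two-sided 5%. The normal formula 2 × (1.960 + 0.842)² × 1.5² / 1² gives 35.3, hence 36. The exact t-test gives 36.3, hence the stated 37 per group. No figure is given for any secondary analysis.

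**Identity.** With two occasions, the one-way repeated-measures F equals the square of the paired t. On a simulated data set of 125 patients, F(1,124) = 97.096 and t² = 97.096, with the same p-value (2.86 × 10⁻¹⁷). This needs no assumption about effect or SD.

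**Illustration: inputs**
- Evaluable patients: 50/50/25 less the plan's 30% drop-out. 50 × 0.7 = 35; 25 × 0.7 = 17.5, taken as 17; total 87.
- SD of change 1.5. This is the plan's NRS value, borrowed because no secondary outcome has a stated SD.
- Before-after test: paired t-test on all 87 patients pooled. Group × time: one-way ANOVA of change scores. Two-sided 5%, 40,000 simulated trials per scenario.

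| Change in verum / control / control of control | Before-after test rejects | Group × time rejects |
|---|---|---|
| 0 / 0 / 0 | 4.8% | 5.0% |
| 0.5 / 0.5 / 0.5 | 87% | 5.0% |
| 1 / 1 / 1 | >99.9% | 4.8% |
| +0.5 / −0.5 / 0 | 4.0% | 69% |

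Analytic checks:
- Row 3: noncentrality 1 / (1.5/√87) = 6.22 on 86 df gives 0.99999.
- Row 4: noncentrality (35 × 0.25 + 35 × 0.25) / 2.25 = 7.78 on 2 and 84 df gives 0.688.

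**Range of SD, 1.0 to 2.5.** With equal 1-point change the before-after test rejects in 100% to 96% of trials, and group × time stays near 5%. With +0.5/−0.5/0 the before-after test rejects in 3% to 5%, against 97% to 29% for group × time.

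**Gender.** Assume near-equal sexes, a verum change of +1 in one sex and −1 in the other, and no change in the controls. The before-after test rejects in 3% of trials and the verum-versus-control × gender interaction in 79%. That is a 2-point interaction. Its standard error is 1.5 × √(4/17.5) = 0.717, so power is about 78% for 2 points but only 28% for 1 point.

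**Arms analysed separately.** With 37 patients per arm and the same 0.5-point change everywhere, verum is significant and sham is not in 24.5% of trials. Reading that pattern as a treatment effect would be wrong about one time in four.

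**The case against.** The strongest reply is that the authors meant a mixed ANOVA and misnamed it. The objectives ask between-group questions, gender is listed for the analysis, and with two time points Bonferroni has no time contrasts to correct. That reading is plausible. But the text says one-way and names no between-patient factor, so a reader who follows it runs the wrong test, and one who guesses chooses the model without a prespecified rule.

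Other points stand in part:
- **Painkillers.** That question names no comparator, so a before-after test answers its literal wording, though not whether the device caused any change. The defect concerns the group and gender questions.
- **Pooling.** The before-after figures pool the arms, which the plan does not specify. Run per arm, the test rejects in verum in 48% of trials in the +0.5/−0.5/0 case. There is still no comparison between arms.
- **Cancelling scenarios.** That case and the gender case are built so that effects offset. With verum +1 and both controls 0, the pooled test rejects in about 66% of trials and group × time in 77%, a much smaller gap. False attribution when all arms improve is the main risk.
- **Borrowed SD.** The value 1.5 is on the NRS scale; RMDQ, NDI and ROM have other scales. The figures show direction and rough size only.

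**Conclusion.** The concern holds: the method is wrong as written. Confidence is high for the wording; what the authors intended cannot be known from the documents. The central point, that the named test has no group or gender term, rests on the two-occasion schedule and the parallel design and on no assumed number. Under the illustrative assumptions, a uniform 1-point improvement with no device effect would be declared significant almost always, instead of in 5% of trials. The primary analysis is unaffected. This should be fixed before the secondary results are analysed.

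**What to change.** Replace the method for the secondary parameters with one prespecified model that contains group. Suggested text:

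> Each SF-MPQ pain quality or score, RMDQ, NDI and each cervical and lumbar ROM measure is analysed by ANCOVA of the final value, with group (verum, control, control of control) as factor and the baseline value as covariate. Pairwise group contrasts are reported with Bonferroni correction over a family (contrasts, outcomes, pain qualities) listed before the data are analysed. For the gender question, gender and group × gender are added and the interaction is tested; this is exploratory because power is low. Change in medication is also compared between groups, including a verum-control contrast, if a change is to be attributed to the device.

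A group × time mixed ANOVA is an acceptable alternative. The Bonferroni correction stays, and adjustment across outcomes should not be dropped by default.

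The cost is one paragraph and a little analysis time, using data already collected and SPSS, which the plan names. The Bonferroni family has a price. For a 1-point verum-control difference in change (SD 1.5, 35 per arm), the standard error is 1.5 × √(2/35) = 0.359. ANCOVA multiplies the variance by (1 + r)/2, which is 0.75 at an assumed before-after correlation r of 0.5.

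| Family | Level per test | Power, change score | Power, ANCOVA |
|---|---|---|---|
| Unadjusted | 0.05 | 79% | 89% |
| 3 contrasts, one outcome | 0.05/3 = 0.0167 | 64% | 78% |
| 3 contrasts × 4 outcomes | 0.05/12 = 0.0042 | 44% | 61% |

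Unadjusted ANCOVA power runs from 93% to 85% for r from 0.3 to 0.7. The last row counts SF-MPQ and ROM once each. Counting every pain quality and ROM measure enlarges the family: with an assumed 24 to 45 tests, change-score power falls to between 36% and 29%. The family should therefore be chosen deliberately and written into the plan.

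### The Bonferroni correction for the secondary outcomes has no stated family, number of tests or adjusted alpha, and two of its three possible readings leave error across outcomes uncontrolled.

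*Combined protocol and SAP*

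**What the plan says.** The only multiplicity rule for secondary outcomes is one clause in the Statistical analysis section: they "are analyzed using RM-One Way ANOVA and Bonferroni correction". The list it governs is given by way of example: "Secondary parameters (e.B. differences in the individual pain qualities in the SF-MPQ; gender-specific differences in SF-MPQ, Roland-Morris Test/Neck Disability Index, ROM; Change in drug dosage". The significance level, "A significance level of alpha = 5% (two-sided) is used", appears under the primary parameters. No adjusted level is given for the secondary ones.

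The secondary outcomes under Type of the study are fuller. The first bullet asks about differences "in the individual pain qualities (SF-MPQ), in the Roland-Morris Disability Questionnaire, in the Neck Disability Index, in the spinal range of motion (ROM", against both the control group and the control of the control group. The second asks "Are there gender-specific differences regarding the effect of StimaWELL® regarding SF-MPQ, in the Roland-Morris Disability Index, Neck-Disability Index or ROM". The third asks about the need for painkillers. The last two name no comparison group.

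The table of measures in the time schedule has the pain questionnaire, the disability questionnaires, mobility and medication each assessed "2x (before and after 6 units StimaWELL"), so every secondary outcome has two time points. The section on questionnaires shows that mobility covers both the cervical and the lumbar spine.

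**The concern.** A Bonferroni correction is defined by its divisor. Without a stated family, two analysts could follow this plan faithfully and use different thresholds, and the choice could be made after the data are seen. Because the clause ties the correction to a one-way repeated-measures ANOVA, its most literal meaning is a correction of pairwise comparisons between time points, and here there is only one such pair.

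At stake is the credibility of secondary claims on pain quality, disability, mobility, medication and gender. A report could truthfully call its results Bonferroni-corrected although nothing had been corrected across outcomes, and a reader could not check this against the plan.

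**Working it through.** **The plan's own figure.** The documents contain no divisor or adjusted alpha to reproduce. The only derived figure tied to alpha is the primary sample size: difference 1, SD 1.5, two-sided 5%, 80% power. The exact noncentral-t calculation gives power 0.797 at 36 per group and 0.808 at 37, so the stated 37 reproduces. It does not bear on the secondary tests.

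**Reading 1: over time points.** Two time points give 2 × 1 / 2 = 1 pair, so the threshold is 0.05 / 1 = 0.05. A two-level one-way repeated-measures ANOVA is the paired t-test. In a numerical check with 37 simulated pairs, F = t² = 2.110 and p = 0.155 for both. This reading assumes that the ANOVA has no group factor.

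**Reading 2: over groups.** Three groups give 3 × 2 / 2 = 3 pairs, so the threshold is 0.05 / 3 = 0.0167 within each outcome. A simulation with no true effect used 35, 35 and 17 evaluable patients (50, 50 and 25 less the assumed 30% dropout, rounded down). It gave an error rate of 4.2% per outcome. Across m independent outcomes the rate is 1 − (1 − 0.042)^m: 23% for 6, 32% for 9 and 38% for 11.

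**Reading 3: across outcomes.** The divisor depends on what is counted:

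- Six: SF-MPQ as one score, RMDQ, NDI, cervical ROM, lumbar ROM, medication.
- Eleven: those six plus the gender question on SF-MPQ, RMDQ, NDI and the two ROM measures (6 + 5).
- Sixteen: those eleven plus a second contrast for the five first-bullet outcomes, because only that bullet names both control groups (11 + 5).
- By instrument only: 4 + 4 + 1 = 9.

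Testing single pain qualities or several movements per spinal region would add more, by a number that the documents do not give.

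**Chance of at least one false positive if each test is read at 5%.**

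- Independent tests: 1 − 0.95^m.
- Equal correlation of 0.5 (an assumption): 1 − ∫ [Φ((1.96 − √0.5·u)/√0.5) − Φ((−1.96 − √0.5·u)/√0.5)]^m φ(u) du.

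| m | Independent | Correlation 0.5 | Bonferroni threshold 0.05/m |
|---|---|---|---|
| 6 | 26.5% | 20.7% | 0.0083 |
| 9 | 37.0% | 26.9% | 0.0056 |
| 11 | 43.1% | 30.4% | 0.0045 |
| 16 | 56.0% | 37.4% | 0.0031 |

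A simulation of 20,000 runs at correlation 0.5 agrees for uncorrected testing (20.4% for 6 and 30.4% for 11). It gives 4.2% and 3.8% with Holm's procedure.

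**The case against.** The strongest reply is that the plan does promise a correction and never says that it runs over time points. That is right. A reader might infer that the correction divides by one, so that the secondary tests are in effect uncorrected. The documents do not support this as a statement of fact: it is one reading of three, and it fails if the ANOVA has a group factor. What stands is that the group reading does not control error across outcomes either, and that the remaining reading lacks a count.

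A reader might also infer that the outcome list is open-ended and that no divisor could exist before the data are seen. This too goes too far. The analysis section's list is illustrative, but the objectives name the instruments, so a divisor could be settled from them in advance. What is missing is the number of tests within those instruments.

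Nor does the size support saying that a false secondary claim is more likely than not. One could reach 22 tests, and 68%, by doubling all eleven for the two control groups. The gender and painkiller questions name no control group, however, and contrasts that share the verum arm are not independent. Counts of 6 to 11 give roughly 20% to 43%. Moreover, contrasts with the control groups are not what a purely before-and-after ANOVA tests, so these figures describe the questions in the objectives each tested at 5%.

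Finally, Holm over Bonferroni is a gain in efficiency, not the repair of an error. A fixed list with a plain Bonferroni divisor, or labelling all secondary analyses exploratory, would also close the gap.

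**Conclusion.** The concern holds in this limited form: a correction is named but cannot be carried out as written, because its family, count and threshold are missing. Two of the three readings give no control across outcomes, and the third needs a number that the plan does not supply.

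If each test is read at 5%, the chance of at least one false secondary finding is about 26% for 6 tests and 43% for 11 under independence, and about 20% and 30% at correlation 0.5. It is about 56% for 16 independent tests and passes one half only in that last case. The counts treat the SF-MPQ as one score and each spinal region as one mobility measure. The correlation is assumed.

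The primary comparison is untouched. This should be corrected, but it does not threaten the main conclusion.

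**What to change.** Before unblinding, replace the sentence with three statements:

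1. **A closed, counted family** of verum-versus-control differences, for example SF-MPQ total, RMDQ, NDI, cervical ROM, lumbar ROM and drug use (m = 6). Its membership is the sponsor's choice, provided it is fixed in advance. In choosing, the sponsor should reconcile drug use as an outcome with the inclusion criterion on constant pain medication.
2. **Holm's step-down procedure** across that family at an overall two-sided 5%. It controls the same error rate as Bonferroni and never rejects less.
3. **Everything else as exploratory**: single pain qualities, gender differences and comparisons with the control of the control group, reported as estimates with 95% confidence intervals and no significance claim.

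This needs no new data or patients. It costs power per secondary outcome, which the plan already accepts by naming Bonferroni. As an illustration, take 35 evaluable patients per main arm (50 × 0.7) and carry the primary assumption of 1 / 1.5 = 0.67 SD over to all six outcomes; the documents give no secondary effect sizes. Power per outcome is then about 79% uncorrected and 54% with Bonferroni at 0.05/6 (exact t). Simulated mean power with Holm is about 63% to 68%, depending on the test used. The other cost is that the exploratory comparisons can no longer be claimed as significant.
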